### **5. SELECTION OF TRIAL POPULATION**

#### 5.1 Inclusion Criteria

To be eligible for this study, subjects must meet all the following:

#### Age

1.  $\geq 18$  to  $\leq 80$  years old inclusive at the time of signing the Informed Consent Form (ICF).

### **Type of Subjects**

- 2. In stable and good general health, without significant medical illness, based on medical history, physical examination, and vital signs at screening based on investigator judgement.
- 3. Body mass index (BMI)  $\geq$  17.0 and  $\leq$  35.0 kg/m2 at screening.
- 4. Available for all planned visits and tele-health appointment, and willing to complete all protocol-defined procedures and assessments (including ability and willingness to swallow multiple small enteric-coated tablets per study dose).

#### **Gender and Reproductive Considerations**

- 6. Male or female subjects
  - a. Female subjects must not be breastfeeding and must provide a negative pregnancy test at screening and pre-dose.
  - b. Female subjects must fulfill one of the following criteria:
    - i. At least 1 year post-menopausal (defined as amenorrhea for  $\geq$  12 consecutive months prior to screening without alternative medical cause) or surgically sterile.
    - Female subjects of childbearing potential must be willing to use a highly effective form of contraception for 30 days prior to initial vaccination and until 60 days after last vaccination. Acceptable forms are oral, implantable, intrauterine, transdermal, intravaginal, injectable, double barrier or abstinence (subjects using diaphragms must also use condom). The form of contraception must be approved by the investigator.
    - iii. Male subjects must agree to practice abstinence from heterosexual intercourse or to use an effective method of birth control as noted above from first vaccination to 60 days after last vaccination. Male subjects must agree to refrain from donating sperm and practice abstinence from all intercourse or to use an effective method of double barrier birth control or condom as noted above from first vaccination to 60 days after last vaccination.

#### **Informed Consent**

6. Capable of understanding and giving signed informed consent which includes compliance with the requirements and restrictions listed in the ICF and in the protocol.
# **Exclusion Criteria**

The subjects must be excluded from participating in the study if they meet any of the following:

- 1. Known clotting/bleeding issues and/or personal and family history with increased risk of bleeding or clotting. -
- 2. Presence of significant uncontrolled medical or psychiatric illness (acute or chronic) including institution of new medical/surgical treatment or significant dose alteration for uncontrolled symptoms or drug toxicity within 3 months prior to screening and reconfirmed at baseline.
- 3. Cancer, or treatment for cancer or any procedure or preventive medication for cancer or to prevent recurrence, within past 3 years (excluding fully treated and resolved basal cell carcinoma or squamous cell carcinoma)
- 4. Presence of immunosuppression or medical condition possibly associated with impaired immune responsiveness, including diabetes mellitus- type 1 and 2
- 5. Left blank intentionally.
- 6. History of irritable bowel disease or other inflammatory digestive or gastrointestinal condition that could affect the distribution/safety evaluation of an orally administered vaccine targeting the mucosa of the small intestine. Such conditions may include but are not limited to:
  - a. Any history of:
    - i. GI malignancy
    - ii. malabsorption
    - iii. pancreatobiliary disorders
    - iv. inflammatory bowel disease
    - v. irritable bowel disease
    - vi. hiatal hernia
    - vii. surgical resection
  - b. History of diagnosis or treatment in past 5 years of:
    - i. esophageal or gastric motility disorder
    - ii. gastro esophageal reflux disorder
    - iii. peptic ulcer
    - iv. cholecystectomy
- 7. History of any form of angioedema
- 8. History of serious reactions to vaccination such as anaphylaxis, respiratory problems, hives or abdominal pain
- 9. Diagnosed bleeding disorder or significant bruising or bleeding difficulties that could make blood draws problematic
- 10. Any condition that resulted in the absence or removal of the spleen

- 11. Acute disease within 72 hours prior to vaccination defined as the presence of a moderate or severe illness (as determined by the investigator through medical history and physical exam). (Assessment may be repeated once during Screening Period)
- 12. Presence of a fever  $\geq$  38.0°C measured orally at baseline.
- 13. Any significant hospitalization within the last year which in the opinion of the investigator or sponsor could interfere with study participation.
- 14. Any of the following history or conditions that may lead to higher risk of clotting events and/or thrombocytopenia:
  - a. Family or personal history of bleeding or thrombosis.
  - b. History of heparin-related thrombotic events, and/or receiving heparin treatments.
  - c. History of autoimmune or inflammatory disease.
  - d. Presence of any of the following conditions known to increase risk of thrombosis within 6 months prior to screening:
    - i. Recent surgery other than removal/biopsy of cutaneous lesions
    - ii. Immobility (confined to bed or wheelchair for 3 or more successive days)
    - iii. Head trauma with loss of consciousness or documented brain injury
    - iv. Receipt of anticoagulants for prophylaxis of thrombosis
    - v. Recent clinically significant infection, including hospitalization for COVID-19 infection.
- 15. Any other condition that in the clinical judgement of the investigator would jeopardize the safety or rights of a subject taking the study drug, would render the subject unable to comply within the protocol or would interfere with the evaluation of the study endpoints diagnostic assessments.
- 16. Positive human immunodeficiency virus (HIV), Hepatitis B surface antigen (HBsAg) or Hepatitis C virus (HCV) tests at the screening visit.
- 17. History of GI bleeding including hematochezia (blood in stool) or melena (black stool)
- 18. Positive urine drug screen for drugs of abuse at screening (positive test for marijuana is not exclusionary; however concurrent use of marijuana during the study Active period through Day 29 is prohibited).
- 19. Positive breath or urine alcohol test at screening and baseline.

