#### **3.2 End Points**

#### **3.2.1 Primary End Points**

#### Safety:

- Frequency, duration, and severity of Solicited Symptoms of Reactogenicity (GI and systemic) for 1 week following each study drug dose.
- Frequency, duration, and severity of unsolicited adverse events (AEs) for 28 days following last study drug dose.

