# 6.3 Dosing and Administration of Investigational Product

This study will investigate the safety and immunogenicity of two monovalent NoV oral tableted vaccine candidates (VXA-G1.1-NN and VXA-GII.4-NS) co-administered (bivalent delivery) against a matching placebo arm. All lots of DP will be provided as small white enteric-coated tablets for oral route of administration.

Multiple tablets of study drug will be dispensed to allow delivery of the intended vaccine dose. A matching number of placebo tablets will be dispensed to maintain the study blinding.

Intervention Name	VXA-G1.1-NN	VXA-GII.4-NS	Placebo
Туре	Biologic	Biologic	Matching placebo
Dose	Enteric-coated tablets	Enteric-coated tablets	Enteric-coated tablets
Formulation			
Dosing	Day 1	Day 1	Day 1
Schedule			
Route of	Oral		
Administration			
Administration	Subjects should fast and refrain	from ingesting solid food for at l	east 4 hours prior to oral dosing.
instructions	A trained member of the site study staff will dispense the tablet(s) constituting their assigned		
	dose to the subject. The subjects will swallow the tablets with 360 to 480 mL of water or clear		
	fruit juice (acidic, such as cranberry juice) followed by a light snack (e.g., crackers) at time of		
	dosage administration to aid in tablet transit out of the stomach. Normal food consumption may		
	resume 90 minutes after dosing. For more information refer to the study specific Pharmacy		
	Manual.		
Sourcing	Study drug will be provided to	the sites by the Sponsor or desig	nated representative.

Table 6:Investigational Product Dosing

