# 7.1.2 Procedure to be followed during Active Study Period (Day 1 to Day 29)

It is anticipated that the procedures below will be conducted in a stepwise manner; ensuring that procedures listed prior to administration of the vaccine are conducted prior to that administration for both the open label and randomized groups of the study.

- The Principal Investigator will ensure that all inclusion criteria and none of the exclusion criteria are met on Day1, prior to vaccination.
- A urine pregnancy test will be done for all female subjects prior to dosing.
- A targeted, and symptom-directed physical examination will be done for all subjects during the active study period visits., At a minimum, assessments of the skin, respiratory system, cardiovascular system, and GI (abdomen, liver and spleen) will be included.
- Vital signs will be obtained, including temperature, sitting blood pressure, pulse rate and respiratory rate after at least 5 minutes of rest to the subject during the active study period.
- The subject's number (open label) or randomization number will be noted.
- Site staff member(s) will dispense/administer the investigational product. Please refer to the Pharmacy Manual for further instruction on this process.
- Prior to study drug administration on Day 1, the subject's temperature (oral) will be measured, and a trained member of the site study staff will dispense the tablet(s) constituting the assigned dose to the subject.
- For the subjects enrolled into the open label sentinel study arm, the site staff must observe the subjects at the site, in the ≥18 to ≤80 years old age group, for at least 2 hours after study drug administration for any acute reactions. Any acute reactions are to be recorded in the subject's source documents, on the AE page of the eCRF, and on a serious adverse event (SAE) form, as applicable.
- For the subjects enrolled into the randomized double blind portion study arm, the site staff must observe the subjects at the site, in the ≥18 to ≤80 years old age group for at least 30

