#### Solicited Adverse Events:

Solicited adverse events (AEs) are predefined signs and symptoms of reactogenicity for which the subject is specifically questioned, and which are noted by the subject in their Solicited Symptom Diary, including:

- fever (any temperature 100°F or higher)
- headache

- myalgia (muscle pain)
- abdominal pain
- anorexia (defined and not eating)
- nausea
- vomiting
- diarrhoea
- malaise/fatigue

Subjects will utilize a Solicited Symptom Diary issued on the day of the vaccination to record solicited any TEAE daily for the one week following that administration.

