# 9.1.5 Time Period and Frequency for Collecting AE, AESI, NOCIs, and SAE Information

All AEs AESIs and NOCIs will be collected from the first dose of study product until the follow-up visit at the timepoints specified in the SoA (Table 1).

Medical occurrences that begin before the start of study drug but after obtaining informed consent will be recorded as medical history/current medical conditions, not as AEs if it does not have a causal relationship with study participation. There are two situations to note as below.

- 1. If the medical occurrence causes the subject to be excluded from the study, then it must be reported by the investigator. This event will then need to be classified as an "AE not related to the study drug."
- 2. If the medical occurrence is the result of a protocol-specified intervention (prior to study drug dose), including but not limited to washout or discontinuation of usual therapy, diet, or a procedure then these must be reported appropriately as an AE (solicited and unsolicited), SAE, AESI, NOCI, and other reportable safety events by the Investigator.

All SAEs will be recorded and reported to the Sponsor or designee immediately and under no circumstance should this exceed 24 hours of being available. The Investigator will submit any updated SAE data to the Sponsor within 24 hours of it being available.

Investigators are not obligated to actively seek information on AEs or SAEs after conclusion of the study participation. However, if the Investigator learns of any SAE, including a death, at any time after a subject has been discharged from the study, and the Investigator considers the event to be reasonably related to the study drug or study participation, the Investigator must promptly notify the Sponsor.

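### Eight of the nine solicited symptoms are not graded before dosing on Day 1, so mild symptoms that were already present and persist can enter the primary reactogenicity rates

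*Combined protocol and SAP*

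**What the plan says.** - **Eligibility.** Section 5.1, criterion 11, excludes "Acute disease within 72 hours prior to vaccination defined as the presence of a moderate or severe illness". Mild illness is not named. Criterion 12 excludes fever at or above "38.0°C measured orally at baseline". Criterion 15 lets the investigator exclude a condition that "would interfere with the evaluation of the study endpoints diagnostic assessments".
- **Day 1 before dosing.** Table 1 schedules medical history, a targeted examination and vital signs. Section 7.1.2 adds: "Prior to study drug administration on Day 1, the subject's temperature (oral) will be measured". Neither place asks for the Table 11 symptoms to be graded before the tablets.
- **Diary.** Section 9.1.1 states: "Subjects will utilize a Solicited Symptom Diary issued on the day of the vaccination to record solicited any TEAE daily for the one week". Section 7.1.2 has the subject record symptoms after administration. Table 8 also heads the solicited column as TEAE and names the diary as its reporting method.
- **Events that start before dosing.** Under section 9.1.5 these "will be recorded as medical history/current medical conditions, not as AEs", with stated exceptions for events related to study participation.
- **Endpoint and analysis.** The primary endpoint in section 3.2.1 is: "Frequency, duration, and severity of Solicited Symptoms of Reactogenicity (GI and systemic) for 1 week following each study drug dose". Section 11.5.2 summarizes it by severity for Day 1 through Day 8, with counts, percentages and Clopper-Pearson intervals. It says missing diary data are not imputed. It is silent on symptoms present at dosing.

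**The concern.** Calling a symptom treatment-emergent requires knowing whether it was there, and at what grade, before treatment. For headache, myalgia, abdominal pain, anorexia, nausea, vomiting, diarrhea and malaise/fatigue, the plan collects no graded pre-dose value. The rule in section 9.1.5 therefore cannot be applied to diary data. A mild headache present on the morning of Day 1 and still present that evening looks in the diary like one that began after the tablets.

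At stake are the absolute frequency, severity and duration of solicited symptoms. These are primary, and the primary objective uses safety results in choosing the Phase 3 dose level. Duration is affected as well as frequency, because a carried-over symptom has no post-dose onset from which to count. The ten sentinels have no concurrent placebo against which the SMC could read such entries.

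**Working it through.** The plan states no background symptom rate, and its sample size is not based on formal testing, so there is no planned figure to reproduce. What follows is an illustration.

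**Inputs.** Arm sizes are 50, 50 and 25, plus 10 sentinels (section 11.2). The other values are assumptions:
- b = share of subjects with a given mild symptom at dosing that persists into the diary: 5% to 15%, with 10% as the worked case.
- v = rate of new post-dose symptoms: 30% on active, 15% on placebo.
- b is the same in all randomized arms in expectation and independent of new onset.

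**Observed rate** = 1 − (1 − v)(1 − b) = v + b(1 − v).
- Active, b = 10%: 1 − 0.70 × 0.90 = 37.0%
- Placebo, b = 10%: 1 − 0.85 × 0.90 = 23.5%

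**Difference** = (1 − b) × true difference.
- 0.90 × 15.0 = 13.5 points (37.0 − 23.5), a loss of 1.5 points.
- The ratio falls from 30/15 = 2.0 to 37.0/23.5 = 1.57.

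**Precision at the true rates.** 1.96 × √(0.30 × 0.70/50 + 0.15 × 0.85/25) = 1.96 × √(0.0042 + 0.0051) ≈ 0.19, a half-width of about 19 points.

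**Counts per active arm of 50.**
- Subjects carrying the symptom over: 50 × 0.05 = 2.5 to 50 × 0.15 = 7.5.
- Net excess at v = 30%, since some would have had a new symptom anyway: 2.5 × 0.70 = 1.75 to 7.5 × 0.70 = 5.25.

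**One arm's displayed rate.** With v = 20% and b = 5%, the rate moves from 20% to 0.20 + 0.05 × 0.80 = 24%. That is 10/50 (exact 95% CI 10.0% to 33.7%) becoming 12/50 (13.1% to 38.2%).

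**Sentinels.** The chance that at least one of 10 carries over a given symptom is 1 − 0.95^10 = 40% to 1 − 0.85^10 = 80%.

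**Fever.** Section 9.1.1 solicits fever from 100°F (37.8°C). Table 11 grades from 100.4°F (38.0°C), and criterion 12 excludes at 38.0°C. A pre-dose reading of 100.0 to 100.3°F is eligible, meets the section 9.1.1 definition and is normal in Table 11.

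**The case against.** The strongest case is that the plan already points the right way. It labels solicited events TEAEs and sends pre-dose occurrences to medical history. It also takes a history, an examination and a temperature on Day 1. Investigators review diary data and assess relationship to study drug, entries marked Grade 3 are checked for another cause, and criterion 15 is available. The placebo arm measures background, the distortion is small against the intervals, no hypothesis test is planned, and a derivation rule could go into the later SAP.

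Much of this stands, and it rules out several stronger readings:
- *The plan counts pre-existing symptoms by design.* It does not. What is missing is the link from the TEAE label and section 9.1.5 to the diary and section 11.5.2.
- *None of the nine symptoms has a pre-dose measure.* Fever has one, and its own exclusion.
- *Background symptoms appear as a vaccine effect.* Placebo carries the same expected background, so the randomized difference shrinks and is not inflated.
- *A carried-over symptom could halt the study after the sentinels.* The solicited-symptom rule in section 10.2 needs two or more subjects with the same treatment-related symptom of grade 3 or above. Sentinels are also outside the Safety set in Table 9, which is limited to randomized subjects.
- *The pre-dose fast adds symptoms.* It applies to every arm, and no document links it to symptoms.

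What does not stand is deferral to the SAP. A derivation can be written later, but a pre-dose grade that was never collected cannot be recovered. History and examination findings are not on the Table 11 scale, so they cannot show a rise in grade. Required review for another cause is specific to Grade 3 entries, whereas this carry-over is mild.

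**Conclusion.** The gap is real but modest. The plan intends solicited symptoms to be treatment-emergent, yet for eight of nine it collects nothing graded that could show this, and the primary summary has no new-or-worse rule. Absolute rates are overstated by b(1 − v) in every arm: 7.0 points on active and 8.5 on placebo in the worked case. Differences between arms shrink by the factor (1 − b).

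The direction follows from the design, given equal expected b across arms and independence from new onset. The size rests entirely on assumed rates, including the assumption that symptoms persist after dosing, and could be smaller. Worsening after dosing would still appear in the by-severity tables. This is a cheap improvement to a primary endpoint. It does not undermine the randomized comparison, and it gives no reason to alter criterion 11.

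**What to change.** 1. In Table 1 and section 7.1.2, add one Day 1 entry before the tablets, in the same diary or app, in which the subject grades the Table 11 symptoms. For fever, use the pre-dose temperature already taken.
2. In section 11.5.2, add a summary of solicited symptoms that are new or higher in grade than that entry, with a cross-reference to section 9.1.5. Show it beside the table of all recorded symptoms, so that nothing is hidden.
3. Give the sentinels' pre-dose grades to the SMC with their Day 1 to Day 8 data.
4. Reconcile the fever thresholds in section 9.1.1 and Table 11, so that pre-dose and post-dose fever are classified on one definition.

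The cost is about a minute per subject, one SAP derivation and one extra table. No visit, sample, staff or eligibility change is needed. The diary entry must be in place before dosing, because the data cannot be collected afterwards.

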#### **Prior/Concurrent Therapy**

- 20. Receipt of a licensed vaccine (including any COVID-19 vaccines under emergency use authorization) within 14 days prior to baseline vaccination or planned administration during the study active period (Day 29).
- 21. Use of antibiotics, proton pump inhibitors, H2 blockers or antacids within 7 days prior to study drug administration or planned use during the active study period (Day 29).
- 22. Use of medications known to affect the immune function (e.g., including but not limited to systemic corticosteroids, leukotriene modifiers, and JAK inhibitors) within 2 weeks before study drug administration or planned use during the active study period (Day 29).

- 23. Daily use of nonsteroidal anti-inflammatory drugs within7 days prior to study drug administration or planned use during the active study period (Day 29). Low dose daily ASA < 100 mg for cardio-protection is not exclusionary.
- 24. Administration of any investigational vaccine, drug or device within 8 weeks preceding study drug administration, or planned use within the duration of the study
- 25. Previous participation in a Vaxart Clinical Trial or other NoV vaccine trial unless confirmed receipt of placebo.

#### **Other Exclusions**

- 26. Donation or use of blood or blood products within 30 days prior to study drug administration or planned donation during the active study period (Day 29).
- 27. History of drug, alcohol, or chemical abuse within 1 year of screening.
- 28. History of hypersensitivity or allergic reaction to any component of the investigational vaccine, including but not limited to fish gelatin allergy.

## 5.2 Early Termination/ Withdrawal criteria

In case of Early Termination (ET) prior to Day 8, all procedures marked as 'early termination assessments' should be completed as shown in the SoA (Table 1).

Subjects have the right to withdraw from the study at any time and for any reason without prejudice to their future medical care by the Investigator or at the institution. A subject may discontinue/withdraw study drug for reasons including but not limited to:

- Adverse event
- Death
- Lost to follow-up
- Physician decision
- Protocol deviation
- Study terminated by Sponsor
- Withdrawal by subject (only for discontinuing study drug, but will remain in study)

The reason for subject discontinuation from study drug will be recorded in the electronic case report form (eCRF).

At the time of withdrawal from the study, the ET visit should be completed, as shown in the SoA (Table 1).

If the subject withdraws consent for disclosure of future information, the Sponsor may retain and continue to use any data collected before such a withdrawal of consent.

Vaxart Inc		
VXA-NVV-202	Version	2.0

If a subject withdraws from the study, he/she may request destruction of any samples taken and not tested, and the Investigator must document this in the site study records.

